	Appendix C : EORTC QLQ-C30	

SCHEMA

M =	-26
11-	50

1.0 **OBJECTIVES**

1.1. Primary Objective:

- Progression free survival (PFS) at 4 months, as measured by Response Evaluation Criteria in Solid Tumors (RECIST).

1.2 Secondary Objectives:

- Objective response rate [compete response (CR), partial response (PR)]
- Clinical benefit [CR +PR + Stable disease ≥ 6 months]
- Assessment of toxicity
- Assessment of compliance with medication adherence
- Assessment of quality of life
- Assessment of bone health

1.3 Exploratory Objectives:

- Serial measurement of serum estradiol, estrone and estrone sulfate.

[figure not shown]
- To investigate treatment resistance (e.g. expression of amphiregulin, EGFR), using molecular

and immunohistochemical analyses of blood and tumor samples of preand post- (when available) treatment tissues. Microarraay analyses to quantitate the expression of specific estrogen-responsive genes (e.g. TTF1 and (PDZk1) will also be performed.

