2.0 BACKGROUND AND RATIONALE

The efficacy of aromatase inhibitors (AI) in the treatment of postmenopausal women with hormone receptor positive, metastatic breast cancer (MBC) is undisputed. In this regard, prior randomized clinical trials have documented the superiority of exemestane (EXE) over tamoxifen, as first line therapy [1] and the superiority of EXE over megestrol acetate, as second line therapy after tamoxifen failure [2]. Prior phase II studies have also documented the efficacy of EXE in the treatment of MBC after failure of several lines of prior hormonal therapies [3], including prior exposure to nonsteroidal AIs [4, 5]. While the utility of EXE has been proven with respect to several important clinical indicators (e.g. response rate, time to progression, median survival time and median duration of response), eventually all patients will develop disease progression due to the development of acquired resistance to further treatment. In addition, as has recently been reported, some patients with breast cancer may derive less than maximal benefit from AI therapy due to noncompliance because of musculoskeletal-related adverse effects [6, 7]. The aim of this research proposal, therefore, is to determine whether there may be an effective strategy to delay the time to development of resistance to EXE in the treatment of MBC, while minimizing potential toxicities and ensuring patient compliance with treatment.

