5.5 Exemestane Drug Diary

To assess compliance with treatment, all patients will be supplied with a calendar of the treatment schedule at the start of each new cycle and will be instructed to track their daily consumption of EXE at home. Completed calendars will be collected at the end of each cycle of treatment.

6.0 STATISTICAL CONSIDERATIONS

6.1 Maximum Accrual: 36 Subjects

While toxicity is safely assumed to be reduced, the improvement in PFS is less clear and interim stopping conditions in case the PFS is dramatically worse than historical data [5], are incorporated in the design. The following design operating characteristics were calculated by the method of Simon, but the specific design chosen differs slightly from the Optimum or Minimax design to take into consideration the sawtooth nature of the power function [18, 19]. Patients will be defined as a "success" or "failure" based on whether they have obtained the appropriate benchmark for median PFS (see below). An interim analysis will be performed at 21 subjects. If fewer than six of the first 21 subjects are a "success", the study will be stopped for futility. If fewer than fourteen patients out of the 36 subjects are a success this will also be suggestive that this regimen does not warrant further study. This design discriminates between an encouraging "success" rate of 50% and a discouraging "success" rate of 30%. The probability of early stopping if the true success rate is 50%, is 1% whereas the probability of early stopping if the true success rate is 30%, is 36%. The overall type II error for the decision on whether or not the treatment is promising is 7%, whereas the type I error is less than 17%, when comparing a discouraging success rate of 30% to an encouraging rate of 50%.

For second or third line patients (as was done prior to the amendment to include first line patients) if patients are progression-free at the 4 month evaluation this will be considered a success. Based on recent publication (e.g. Paridaens, et al , Vol 26, No. 30, pp-4883-4890, JCO 2008) the median PFS for first line patients on EXE is approximately 10 months. As a result, we will view a "success" for first line patients if they are progression-free at 10 months.

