Patients who are not first line will be assigned to Treatment Arm 1. Patients who are first line will be accrued to treatment Arm 2. These arms are used simply as a convenience for easier determination of the primary endpoint, and no specific accrual goals are made for each treatment arm, with a total goal of 36 subjects.

While it is assumed that reduced exposure to EXE results in fewer and less severe drugrelated toxicities, a sufficient sample size must be accrued in order to obtain a reasonable estimate of the frequency of treatment related toxicities. One benchmark will look at the incidence of joint disorders, reported by Gradishar [5], at approximately 30%. A onesided exact binomial test with a nominal 10% significance level, will have 81% power to detect a difference from a historical 30% complication rate, to a 15% complication rate with 36 subjects. Generally, however, if the PFS is equivalent to historical data, this will be considered successful, based on the assumption that reduced drug exposure will result in less toxicity. While progression free survival (time to progression or death) at 4 months (and 10 months) is calculated as a binomial (all treated patients will count and patients lost to follow-up before 4 months (10 months for first line) will count as a failure), progression-free survival will also be reported using the method of Kaplan-Meier.

6.2 Correlative Analysis

With 36 patients, correlative analysis will be exploratory in nature. No attempt will be made to adjust for multiple comparisons (except as part of standard microarray analysis) and this will be noted in any report. Changes from baseline and comparison between responders and non-responders, will be summarized. We will also do a more refined analysis of 1st line, second line and third-line patients to explore the potential impact of EXE in these different patient populations.

6.3 Reporting of results

• All patients included in this study must be assessed for response to treatment, even if there are major protocol treatment deviations or if they are later determined to be ineligible. Each patient will be assigned one of the following categories: 1) complete response, 2) partial response, 3) stable disease, 4) progressive disease, 5) early death from malignant disease, 6) early death from toxicity, 7) early death because of other cause, or 9) unknown (not assessable, insufficient data).

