8.0 DRUG INFORMATION

8.1 Description

EXE is an oral, irreversible, steroidal aromatase inactivator, structurally similar to the natural substrate, androstenedione. In postmenopausal women, estrogens are produced primarily by the conversions of androgens into estrogens through the aromatase enzyme in peripheral tissues. By acting as a false substrate and irreversibly binding to the active site of the aromatase enzyme, EXE causes inactivation of the aromatase enzyme,

resulting in significant inhibition of circulating estrogen concentrations in postmenopausal women, but has no detectable effect on adrenal biosynthesis of corticosteroids or aldosterone. In postmenopausal breast cancer patients treated with 25 mg of EXE daily, whole body aromatization was suppressed by greater than 90%. EXE is currently approved by the FDA for use in the treatment of postmenopausal women with advanced breast cancer, whose disease has progressed following tamoxifen therapy. EXE is also approved for use as adjuvant therapy for postmenopausal women with estrogen receptor positive breast cancer. The recommended dose of EXE is 25 mg orally once daily after a meal.

8.2 Toxicology

In clinical trials of 1058 postmenopausal women with advanced breast cancer, daily doses of EXE consisting of 25 mg, was generally well tolerated and adverse events were usually mild to moderate. Adverse effects of EXE which have been reported among postmenopausal women receiving this therapy in either the adjuvant or metastatic setting, include:

More Common

Endocrine/metabolic: diaphoresis (6-17.8%), hot sweats (13-32.9%) Gastrointestinal: nausea (8.5-18%), diarrhea (4-9.6%), vomiting (7%)

Musculoskeletal: arthralgia (14.6-28.8%), myalgia (5.5%), osteoporosis (4.6%), pain in limb (9%), osteoarthritis (5.9%) Neurologic: headache (6.9-13.1%), insomnia (11-13.7%), dizziness (8-9.7%) Constitutional: fatigue (11-22%), asthenia (6%) Dermatologic: alopecia (15.1%), dermatitis (8.2%) Psychiatric: depression (6.2-13%), anxiety (4.1-11%)

Severe

Cardiovascular: heart failure (0.4%), myocardial infarction (1.6%) Musculoskeletal: fracture of bone (4.2%) Neurologic: cerebrovascular accident (6 deaths due to stroke, N=2252) Hematologic: thromboembolic event (0.9%)

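### Section 6.1 lets a regimen that only matches historical PFS count as successful on assumed lower toxicity, and gives the planned joint-disorder test no stated role in that conclusion

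*Combined protocol and SAP*

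**What the plan says.** Section 6.1 of the combined protocol and SAP opens by treating the toxicity question as settled: "While toxicity is safely assumed to be reduced, the improvement in PFS is less clear". Its two decision thresholds count PFS successes only: stop for futility with fewer than 6 of the first 21, and regard the regimen as not worth pursuing with fewer than 14 of 36.

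Later in 6.1 the plan says that "a sufficient sample size must be accrued in order to obtain a reasonable estimate of the frequency of treatment related toxicities". It then names a measure: "One benchmark will look at the incidence of joint disorders", with a historical rate of about 30%, a one-sided exact binomial test at a nominal 10%, and 81% stated power against 15% with 36 subjects.

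The next sentence sets the interpretation: "Generally, however, if the PFS is equivalent to historical data", then "this will be considered successful, based on the assumption that reduced drug exposure will result in less toxicity".

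Elsewhere, Section 1.2 lists "Assessment of toxicity" as a secondary objective, and Section 2.0 states the aim as delaying resistance "while minimizing potential toxicities and ensuring patient compliance with treatment".

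**The concern.** A regimen that improves PFS needs no help from toxicity. A regimen that only matches historical PFS does: in 6.1, lower toxicity is the reason given for still calling it successful. That reason is entered as an assumption, although the trial collects the data that bear on it and plans a test with a stated significance level and power. The test has no stated consequence. Nothing says how the conclusion should read if joint disorders do not fall, or rise.

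At stake is how the final conclusion is worded. The report could call the regimen successful on a toxicity-sparing argument that its own joint-disorder result does not support.

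**Working it through.** **Inputs, all from Section 6.1.** PFS rule: at least 6 of 21, then at least 14 of 36; discouraging rate 30%, encouraging rate 50%. Joint disorders: n = 36, p0 = 0.30, p1 = 0.15, one-sided, nominal 10%.

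**1. Reproduce the PFS design.** With X1 ~ Bin(21, p) and X2 ~ Bin(15, p):

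- P(stop early) = P(X1 ≤ 5)
- P(pass) = sum over x = 6 to 21 of P(X1 = x) × P(X2 ≥ 14 − x)

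| True success rate | P(stop early) | Plan | P(pass) | Plan |
|---|---|---|---|---|
| 50% | 1.3% | 1% | 93.0% | 93% (type II error 7%) |
| 30% | 36.3% | 36% | 16.0% | type I error below 17% |

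The PFS figures reproduce.

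**2. Reproduce the joint-disorder test.** For X ~ Bin(36, p), reject when X ≤ c. Size is P(X ≤ c) at p = 0.30 and power is P(X ≤ c) at p = 0.15.

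| c | Size | Power |
|---|---|---|
| 5 | 2.2% | 54.1% |
| 6 | 5.4% | 71.0% |
| 7 | 11.2% | 83.8% |

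The plan states no cut-off. The largest that stays within 10% is c = 6, with 71.0% power. No exact cut-off gives 81%. The normal approximation does: (0.15 − 1.2816 × √(0.30 × 0.70/36)) / √(0.15 × 0.85/36) = 0.876, and Φ(0.876) = 80.9%.

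**3. PFS rule met, joint-disorder reduction not shown.** Take a true success rate of 50%, joint disorders unchanged at 30%, and c = 6. P(reduction not shown) = 1 − 0.054 = 0.946. Under independence, 0.930 × 0.946 = 0.880, or about 88%.

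Independence matters little here. For any dependence, the joint probability lies between 0.930 + 0.946 − 1 = 0.876 and 0.930.

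**4. What tying the toxicity-sparing claim to the test would do.** P(both met) at a 50% success rate, c = 6, under independence:

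| True joint-disorder rate | P(X ≤ 6) | P(both met) |
|---|---|---|
| 30% | 5.4% | 0.930 × 0.054 = 5% |
| 20% | 40.1% | 0.930 × 0.401 = 37% |
| 15% | 71.0% | 0.930 × 0.710 = 66% |

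At 15%, any dependence keeps the last figure between 0.930 + 0.710 − 1 = 64% and 71%.

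**The case against.** The strongest reply is that this is a pilot phase II trial whose only primary objective is PFS. One efficacy endpoint with toxicity reported beside it is a legitimate design, and making joint disorders a second condition for going forward would cost power. That stands, and it is why the PFS thresholds should not change.

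Several stronger readings are tempting, and the documents do not support them:

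- **That toxicity can never alter the verdict.** The sentence begins with a hedge, "Generally, however, if the PFS is equivalent to historical data", which leaves discretion. Death is a PFS event, and loss to follow-up before the benchmark counts as failure, so severe toxicity can lower the success count. Section 7 refers to safety stopping rules, without specifying any, and lets the DSMC suspend or terminate the study. None of this gives joint disorders a role in the conclusion. The accurate statement is that no stated rule does so.
- **That the plan permits a claim of reduced toxicity against its own data.** It does not say so. Toxicity is assessed as a secondary objective, and nothing suppresses the result.
- **That the protocol's figures refute the assumption.** The schedule keeps 14 of 21 dosing days while the test looks for a halving, but the assumption is only of fewer and milder toxicities, and a fall from 30% to 20% would satisfy it. Section 8.1 says that by "irreversibly binding to the active site of the aromatase enzyme, EXE causes inactivation of the aromatase enzyme", but it says nothing about toxicity in the off week. The assumption is untested, not contradicted.

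It is also fair to object that 6.1 never ties historical equivalence to 14 of 36. The 88% therefore rests on reading that threshold as the success rule.

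**Conclusion.** The point holds as a fault in how the conclusion is drawn, not in the PFS decision rule. Section 6.1 rests success for a merely equivalent regimen on lower toxicity, plans a test that bears on it, and then gives that test no bearing on the conclusion. The unfavourable case is not remote: if joint disorders are unchanged, PFS success without a shown toxicity reduction is the expected outcome at a 50% success rate (about 88%).

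That size depends on the 50% and 30% rates, on a cut-off of 6 of 36 that the plan does not state, and on 14 of 36 being the success rule. It depends little on independence. The defect is worth correcting before analysis, but it does not invalidate the design.

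**What to change.** In Section 6.1:

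1. Keep 6 of 21 and 14 of 36 unchanged as the decision on further study.
2. Remove the opening assertion that lower toxicity can safely be taken as given.
3. Replace the assumption as the ground for success with: *A regimen that only matches historical PFS will be described as successful on toxicity-sparing grounds only if the planned joint-disorder test is met. Otherwise the conclusion will read: PFS criterion met; reduction in toxicity not shown. The observed joint-disorder rate and its exact confidence interval will be given in either case.* For scale, 11 of 36 (30.6%) has an exact 95% interval of 16% to 48%.
4. State the cut-off as at most 6 of 36, with size 5.4% and power 71%, and correct the 81%. Choosing 7 would raise power to 83.8% but gives a size of 11.2%, above the nominal 10%.

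**Cost.** No new patients or data are needed. The change does make a toxicity-sparing claim harder to reach: at a 50% success rate, 93% on PFS alone becomes about 66% with joint disorders at 15%. A smaller real benefit would often be missed, since a fall to 20% meets the test only about 40% of the time. A failed test must therefore be worded as a reduction not shown, never as evidence of no reduction.

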7.0 DATA AND SAFETY MONITORING

7.1 Definition of Risk Level

This is a Risk Level 3 study, as defined in the "City of Hope Data and Safety Monitoring Plan", http://www.coh.org/dsmc/Pages/forms-and-procedures.aspx because it is a pilot, Phase II clinical trial where the risks are at least balanced by the potential benefit to subjects and the importance of the knowledge that may result.

7.2 Monitoring and Personnel Responsible for Monitoring

The Protocol Management Team (PMT), consisting of the PI, Collaborating Investigator, CRA/protocol nurse and statistician, is responsible for monitoring the data and safety of this study, including implementation of any stopping rules for safety and efficacy.

Data and safety will be reported to the COH DSMC using the PMT report and submitted according to the timelines in Table 1 below. Protocol specific data collection will include the following items: summary of accrual, adverse events, and treatment related mortality.

Risk Level	Phase	Standard Reporting Requirement
RL 1, RL2, and Compassionate Use Studies	No reports required	

3	I	Every 3 months from activation date, as indicated in MIDAS
3	Pilot, Feasibility, II-IV	Every 6 months from activation date, as indicated in MIDAS
4	Pilot, Feasibility, I-IV	Every 3 months from activation date, as indicated in MIDAS

.

7.3 Definitions

Adverse event (AE) - An adverse event is any untoward medical experience or change of an existing condition that occurs during or after treatment, whether or not it is considered to be related to the protocol intervention.

Unexpected Adverse Event [21 CFR 312.32 (a) – An adverse event is unexpected if it is not listed in the investigator's brochure and/or package insert; is not listed at the specificity or severity that has been observed; is not consistent with the risk information described in the protocol and/or consent; is not an expected natural progression of any underlying disease, disorder, condition, or predisposed risk factor of the research participant experiencing the adverse event.

Expected Adverse Event - Any event that does not meet the criteria for an unexpected event OR is an expected natural progression of any underlying disease, disorder, condition, or predisposed risk factor of the research participant experiencing the adverse event

Serious Adverse Event (SAE) [21 CFR 312.32] is defined as *any expected or unexpected adverse event* that results in any of the following outcomes:

- Death
- Is life-threatening experience (places the subject at immediate risk of death from the event as it occurred)
- Unplanned hospitalization (equal to or greater than 24 hours) or prolongation of existing hospitalization
- A persistent or significant disability/incapacity
- A congenital anomaly/birth defect
- Secondary Malignancy
- Any other adverse event that, based upon appropriate medical judgment, may jeopardize the subject's health and may require medical or surgical intervention to prevent one of the outcomes listed above (examples of such events include allergic bronchospasm requiring intensive treatment in the emergency room or at home, blood dyscrasisas of convulsions that do not result in inpatient hospitalization, or the development of drug dependency or drug abuse).

Unanticipated problem (UP) – Any incident, experience, or outcome that meets all three of the following criteria:

- 1. Unexpected (in term nature, severity, or frequency) given the following: a) the research procedures described in the protocol-related documents such as the IRB approved research protocol, informed consent document or Investigator Brochure (IB); and b) the characteristics of the subject population being studied; AND
- 2. Related or possibly related to participation in the research (possibly related means there is a reasonable possibility that the incident, experience, or outcomes may have been caused by the drugs, devices or procedures involved in the research); **AND**
- 3. Suggests that the research places subjects or others at greater risk of harm (including physical, psychological, economic, or social harm) than previously known or recognized.

7.4 Reporting of Unanticipated Problems and Adverse Events

Unanticipated Problems: Most unanticipated problems must be reported to the COH DSMC and IRB **within 5 calendar days** according to definitions and guidelines at http://www.coh.org/hrpp/Pages/hrpp-policies.aspx. Any unanticipated problem that occurs during the study conduct will be reported to the DSMC and IRB by submitting electronically in iRIS (http://iris.coh.org).

Serious Adverse Events - All SAEs occurring during this study, whether observed by the physician, nurse, or reported by the patient, will be reported according to definitions and guidelines at http://www.coh.org/hrpp/Pages/hrpp-policies.aspx and Table 2 below. Those SAEs that require expedited reporting will be submitted electronically in iRIS (http://iris.coh.org/).

Adverse Events - Adverse events will be monitored by the PMT. Adverse events that do not meet the criteria of serious OR are not unanticipated problems will be reported only in the protocol continuation reports and PMT report (see Table 2 below).

Table 2: City of Hope Adverse Event and Unanticipated Problem Reporting Timelines for the DSMC and IRB

Required Reporting Timeframe to DSMC		
Attribution	UNEXPECTED	EXPECTED

Required Reporting Timelines to DSMC for AE/SAEs Investigator Initiated Studies

	Death while on active treatment or within 30 days of last day of treatment	
Possibly, Probably, Definitely Unlikely, Unrelated	5 calendar days	
	Death after 30 days of last	t active treatment/therapy
Possibly, Probably, Definitely	5 calendar days	No reporting required
Unlikely, Unrelated	No reporting required	No reporting required
	Grades 3 and 4 AND meeting the definition of "serious"	
Possibly, Probably, Definitely	5 calendar days	10 calendar days
Unlikely, Unrelated	5 calendar days	10 calendar days
	Grades 1 and 2 AND resulting in "hospitalization"	
Possibly, Probably, Definitely	5 calendar days	10 calendar days
Unlikely, Unrelated	10 calendar days	10 calendar days

Externally Sponsored Studies

Required Reporting Timeframe to DSMC		
Attribution	UNEXPECTED ¹	EXPECTED
	Death while on active treatment or within 30 days of last day of treatment	
Possibly, Probably, Definitely	No DSMC reporting required - IRB reporting may be necessary	
Unlikely, Unrelated		
	Death after 30 days of las	t active treatment/therapy
Possibly, Probably, Definitely	No DSMC reporting required - IRB reporting may be necessary	
Unlikely, Unrelated		
	Grades 3 and 4 AND meeting the definition of "serious"	
Possibly, Probably, Definitely	No DSMC reporting required - IRB reporting may be necessary	
Unlikely, Unrelated		
	Grades 1 and 2	
Possibly, Probably, Definitely	No DSMC reporting required - IRB reporting may be necessary	

An event determined by the IRB of record to be an Unanticipated Problem (UP) will be communicated to the Investigator and COH DSMC through the COH IRB Operations Director. The DSMC will review the case and make a determination as to whether the study will be suspended, terminated, amended, or allowed to continue without amendment.

Required Reporting Timeframe to IRB of Record								
Attribution	UNEXPECTED	EXPECTED						
	De	ath						
Possibly, Probably, Definitely	5 calendar days	Annual						
Unlikely, Unrelated	Annual	Annual						
	Grades 3 and 4 AND meeting the definition of a UP							
Possibly, Probably, Definitely	5 calendar days	Annual						
Unlikely, Unrelated	Annual	Annual						
	Grade 1 and 2 AND meeting the definition of a UP							
Possibly, Probably, Definitely	5 calendar days	Annual						
Unlikely, Unrelated	Annual	Annual						

Additional Reporting Criteria

Pfizer

In addition to requirements of reporting of adverse events to the COH DSMB and IRB, serious adverse events resulting in death or considered life threatening will be submitted to Pfizer within 24 hours of awareness, via FDA MedWatch Form 3500A-Mandatory Reporting, obtained from the FDA website (http://www.fda.gov/medwatch/report/hcp.htm). The period that serious adverse events will be reported to Pfizer will be from the occurrence after the first dose of EXE, through 28 days after discontinuation of study treatment.

Fax FDA MedWatch Form 3500A to:

Pfizer U.S. Clinical Safety [contact]

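### Section 7.4 joins two conditions with OR where neither/nor is meant, so read literally it limits serious events that are not unanticipated problems, and non-serious unanticipated problems, to periodic reports

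*Combined protocol and SAP*

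**What the plan says.** Section 7.4 has three labelled paragraphs followed by Table 2.

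- **Unanticipated problems.** Most go to the DSMC and IRB within 5 calendar days. The event need not be serious.
- **Serious adverse events.** "All SAEs occurring during this study, whether observed by the physician, nurse, or reported by the patient, will be reported according to" the institutional guidelines and Table 2. The paragraph adds: "Those SAEs that require expedited reporting will be submitted electronically in iRIS".
- **Adverse events.** Those that are not serious "OR are not unanticipated problems will be reported only in the protocol continuation reports and PMT report", with a pointer to Table 2.

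The definitions are in section 7.3. An SAE can be "any expected or unexpected adverse event" with a listed outcome. A UP must meet three criteria together: "Unexpected (in term nature, severity, or frequency) given the following" (the study documents and the population); "Related or possibly related to participation in the research"; and "Suggests that the research places subjects or others at greater risk of harm" than was known before.

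Section 7.2 makes PMT reports due every 6 months for a Risk Level 3 phase II study. A separate rule at the end of section 7.4 sends fatal or life-threatening SAEs to the manufacturer within 24 hours, in addition to DSMC and IRB reporting.

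**The concern.** The third paragraph should cover what is left after the first two, that is, events that are neither serious nor UPs. Joining two negatives with OR gives a much wider set. Any event that fails one test falls under the sentence, and its *only* rules out any other route. A serious event that fails a single UP criterion is then confined to periodic reports, although the paragraph above sends it to Table 2. A UP that is not serious is also caught, against the UP paragraph.

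What is at stake is how soon the DSMC hears of individual events. Staff who apply the sentence as written would hold a reportable event for the next six-monthly report instead of sending it within 5 or 10 days. No endpoint, sample size or error rate is involved.

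**Working it through.** The plan gives no figure to reproduce. The check is one of logic, followed by a count of table cells.

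**Step 1. Events the sentence covers.** Cross *serious* with *UP*:

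| Serious | UP | As written (not serious OR not UP) | Neither serious nor UP |
|---|---|---|---|
| yes | yes | not covered | not covered |
| yes | no | periodic only | not covered |
| no | yes | periodic only | not covered |
| no | no | periodic only | periodic only |

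As written, 3 of the 4 combinations go to periodic reports only. With neither/nor, 1 of 4 does. The second and third rows are the error.

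**Step 2. DSMC limits at issue.** These are the calendar-day limits in the investigator-initiated part of Table 2, with the merged entry for early deaths counted as four cells:

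| Event | Related, unexpected | Related, expected | Unrelated, unexpected | Unrelated, expected |
|---|---|---|---|---|
| Death on treatment or within 30 days | 5 | 5 | 5 | 5 |
| Death after 30 days | 5 | none | none | none |
| Grade 3-4, serious | 5 | 10 | 5 | 10 |
| Grade 1-2, hospitalization | 5 | 10 | 10 | 10 |

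- Cells: 4 × 4 = 16. Cells with a time limit: 16 − 3 = 13.
- A UP must be both unexpected and at least possibly related, so only the first column can hold one: 4 cells.
- Time-limited cells that cannot hold a UP: 13 − 4 = 9.

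Of these 9, 6 are excluded by attribution alone (two in each of three rows). The other 3 are excluded by expectedness, assuming that the table and the first UP criterion use the term in the same way. Without the merged death entry, the count is 13 − 4 = 9 time-limited cells, of which 3 can hold a UP and 6 cannot. Even in a cell that can hold a UP, an event that fails the third criterion is not one and is caught by the sentence.

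**Step 3. IRB limits.** The IRB part of Table 2 has 3 × 4 = 12 cells. Three (unexpected and related) carry 5 days, and 12 − 3 = 9 are annual. Two of those three 5-day rows already require a UP. For most non-UP or unrelated events, periodic reporting to the IRB is therefore what the table asks for. The IRB conflict is limited to non-serious UPs and to an unexpected, related death that fails the third UP criterion.

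**Step 4. Effect of the rewording.** With neither/nor, every SAE and every UP leaves the sentence, and none of the 13 cells is affected. This takes the hospitalization in the last row to be one that meets the SAE definition in section 7.3 (unplanned, 24 hours or more).

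**The case against.** The strongest reply is that no careful reader would apply the sentence literally. It sits in the residual paragraph, follows a sentence covering all SAEs, and points to Table 2 itself. The literal reading would defeat both preceding paragraphs and much of the table. In ordinary English the sentence can be heard as *neither serious nor a UP*. Its two limbs also have a visible source, since DSMC timing turns largely on seriousness and IRB timing largely on UP status. Other safeguards remain: 24-hour reporting to the manufacturer, toxicity calls every three weeks, PMT monitoring, and an institutional policy that the plan links but does not reproduce.

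Most of this stands, and it is why the practical severity is low. It does not remove the error. The pointer leads to a table that disagrees with the sentence, and no clause says which prevails. A safety-reporting rule should not depend on inference.

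A reader might go further in three ways that the documents do not support.

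- *Most SAEs would be delayed.* The plan gives no event counts, and 9 of 13 cells is not a frequency of events.
- *Any serious event that is not a UP would be delayed.* Expected or unrelated deaths after 30 days need no DSMC report, and grade 1-2 serious events without hospitalization have no DSMC row. Neither has a 5- or 10-day limit to breach.
- *The two rules cannot both be followed.* That holds only on the literal reading. On the meaning that context supplies, they agree.

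**Conclusion.** This is a drafting error in an operative safety-reporting rule. Read literally, the sentence in section 7.4 contradicts the SAE paragraph, the DSMC limits in 9 or more of 13 time-limited cells, and the 5-day UP rule. The conflict lies mainly in DSMC reporting.

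The largest delay is about 6 months in place of 5 or 10 days, for an event that occurs just after a PMT report. It is an upper bound that requires staff to apply the sentence literally and disregard the paragraph above it.

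The conclusion about Table 2 assumes that its investigator-initiated part applies. The plan does not label the study expressly, but section 7.2 has the study's own PMT report to the institution's DSMC, which supports that reading. If the externally sponsored part applied, Table 2 would set no DSMC limit to conflict with. The conflicts with the UP rule and with the all-SAEs sentence would remain.

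**What to change.** In the adverse-event paragraph of section 7.4, change the condition to *adverse events that are neither serious nor unanticipated problems* and leave the rest of the sentence as it is. SAEs then follow the SAE paragraph and Table 2, and UPs follow the UP paragraph.

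Do not add a general statement that Table 2 governs. Its DSMC part has no row for non-serious UPs, so such a clause could displace the 5-day UP rule. The 24-hour manufacturer rule is separate and needs no change.

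The cost is a few words at the next amendment. No procedure, form, sample size or analysis changes.
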